### 5.3.4 Other Analyses

#### Analysis plan for Exploratory Aim-1:

Descriptive and graphical statistics will be used to present the distribution of metabolites' concentration markers in the plasma on day 1, Day 7 and 14 using HPLC within each study arm. These markers will also be compared for differential distribution between the arms using Wilcoxon-Mann-Whitney test at each visit. To compare the change over time in these markers, Random Coefficients Models will be utilized where each of these markers will be the dependent variable and study arm and time will be main predictors.

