1. To evaluate the basic pharmacokinetics of TQ Formula main active ingredient (thymoquinone) at same time points (Days 1, 7, and 14) in participants with COVID-19 infection.	Measurement of thymoquinone and metabolites' concentration in the plasma on day 1, Day 7 and 14 using HPLC in patients treated with TQ Formula .	Thymoquinone is the main active ingredient of TQ Formula and the pharmacokinetics of thymoquinone and its' metabolites in the plasma of treated patients are used to correlate with effectiveness of treatment
2. To explore the effect of TQ Formula on inflammatory cytokines, coagulation factors and effector immune cells at same time points (Days 1, 7, and 14) in participants with COVID-19 infection.	Measurement of the inflammatory cytokine production, coagulation factors and the various effector immune cell subsets in the Peripheral Blood Mononuclear Cells (PBMC) of these patients on Day 1, Day 7 and Day 14 using FACS.	The inflammatory cytokines and immunological markers are of importance because of their correlation with disease severity in COVID19.

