9.4.3 ANALYSIS OF THE SECONDARY ENDPOINT(S)

None of the following endpoints depend on the findings of the primary endpoint.

The first secondary endpoint of this clinical trial is the differential change of viral load distribution overtime between the two-study arm. As the viral load will be measured at Baseline, on Day-7, and on Day-14 (and potentially for some patients in Day-4 and Day-10 visits), the outcome variable of interest will be a longitudinal interval-scale measure. To assess the differential behaviour of viral load overtime between the two study arms, Random Coefficients Models will be utilized where viral load will be the dependent variable and study arm and time will be main predictors. Viral load measures may be subjected to some data transformation (e.g., log transformation) to improve the model fit and assumptions as necessitated by model diagnostics. In addressing this objective, all available data will be utilized; that is, in addition to the evaluable patients, data from non-evaluable patients such as data only at baseline visit or data at baseline and Day-10 for example will be used to improve the local fit of the underlying model. To assess differential behavior in total symptom severity score, time*study-arm interaction will be investigated as well.

The percentages of RT-PCR negative/undetectable viral loads between the two study arms will be compared using Fisher's Exact test at Day-7 and Day-14 visits.

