#### 4.1.3 Other Efficacy Endpoints

The endpoints for the exploratory aims are the following:

1. Measurement of thymoquinone and metabolites' concentration in the plasma on day 1, Day 7 and 14 using HPLC in patients treated with TQ Formula.
2. Measurement of the inflammatory cytokine production, coagulation factors and the various effector immune cell subsets in the Peripheral Blood Mononuclear Cells (PBMC) of all patients on Day 1, Day 7 and Day 14 using FACS.

If other analyses are needed beyond the endpoints mentioned above, this plan will be revised.

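### SAP 5.3.4 analyses plasma concentrations in both arms although the endpoint covers only TQ Formula participants, and no SAP analysis relates concentration to outcome

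*SAP*

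**What the plan says.** SAP 4.1.3 defines the first exploratory endpoint as thymoquinone and metabolite levels, measured "using HPLC in patients treated with TQ Formula". The next endpoint in the same list (cytokines, coagulation factors, immune cells) is measured in all patients, so the restriction looks deliberate. The protocol synopsis draws the same line.

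SAP 5.3.4, Exploratory Aim-1, plans three things:

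- Summaries in both arms. Descriptive and graphical methods will "present the distribution of metabolites' concentration markers in the plasma on day 1, Day 7 and 14 using HPLC within each study arm". Parent thymoquinone is not named here.
- A between-arm test: "These markers will also be compared for differential distribution between the arms using Wilcoxon-Mann-Whitney test at each visit".
- A longitudinal model: "To compare the change over time in these markers, Random Coefficients Models will be utilized", in which "each of these markers will be the dependent variable and study arm and time will be main predictors".

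Protocol section 3, in its column justifying the endpoints, says that thymoquinone and metabolite pharmacokinetics "in the plasma of treated patients are used to correlate with effectiveness of treatment". Protocol 9.4.9 leaves the analysis details of both exploratory aims to the SAP.

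**The concern.** The analysis does not match its own endpoint. Protocol 6.1.1 and 6.2.2 say that the placebo has no active ingredient. Comparing study-drug levels with that arm says little about the pharmacokinetics of the product, and the resulting p-value could be read as a finding.

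The same two-arm template is used for Exploratory Aim-2. It suits that aim, because both arms have cytokines and immune cells. It does not suit drug levels: a single time slope shared by a dosed and an undosed arm describes neither.

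The reason given for the measurement, relating exposure to effect in treated patients, has no analysis behind it. Blood would be drawn and assayed without the SAP saying how that question will be addressed.

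**Working it through.** The documents give no figure for this aim, so there is none to reproduce.

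**Inputs.** Allocation is 1:1 (SAP 3.4). Power is based on 20 per arm and planned accrual is 26 to 30 per arm (SAP 3.2). Tests are two-sided at 0.05 (Protocol 9.4.1). Sampling is on Days 1, 7 and 14. Assumptions, not in the documents: placebo values all not quantifiable or flat over time, the slope values, and the simulation variances.

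**1. Between-arm test after dosing.** Suppose every treated participant is quantifiable and no placebo participant is. The exact two-sided Wilcoxon p is 2/C(2n,n):

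| n per arm | Exact p | Normal approximation, placebo values tied |
|---|---|---|
| 20 | 1.5e-11 | 8e-9 |
| 26 | 4.0e-15 | 4e-11 |
| 30 | 1.7e-17 | 1e-12 |

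Complete separation is not needed for significance. If only k treated participants are quantifiable and everyone else is tied, the tie-corrected normal approximation with k = 4 gives p = 0.040, 0.041 and 0.042 at 20, 26 and 30 per arm. The exact p is 2·C(n,k)/C(2n,k). It falls below 0.05 at k = 5 for n = 20 (2 × 15,504/658,008 = 0.047), and at k = 6 for n = 26 (2 × 230,230/20,358,520 = 0.023) and n = 30 (2 × 593,775/50,063,860 = 0.024). A handful of measurable levels is enough, whatever their size.

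**2. Day 1.** Protocol 4.1 lists baseline blood collection ahead of randomization and administration, but does not state timing relative to the first dose. If the sample is pre-dose, neither arm has study drug on board.

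**3. Time slope.** With arm and time only, the same sampling days and equal variances, the common slope is the arm-weighted mean:

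b(common) = [n(TQ)·b(TQ) + n(P)·b(P)] / [n(TQ) + n(P)]

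With b(P) = 0 this is the treated share times b(TQ).

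- 26 and 26: 26/52 = 50%. Simulation with a true treated slope of 0.10 per day gave 0.051 (0.050 with constant placebo values).
- 28 and 28: 50%. Simulation with a true slope of 0.050 gave 0.025; the treated arm alone gave 0.050.
- 26 treated and 22 placebo: 26/48 = 54%. Simulation with a true slope of 0.10 gave 0.057.
- 26 and 26 with an arm-by-time term: 0.104 treated and 0.001 placebo, so no halving.

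Some simulated fits gave convergence warnings; the half-slope result also follows from the algebra.

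**4. Is the arm-by-time term in the plan?** The secondary-endpoint text uses the same arm-and-time phrase and then adds that "time*study-arm interaction will be investigated as well" (Protocol 9.4.3, repeated in SAP 5.3.3 for Aims 1 and 3). SAP 5.3.4 Aim-1 has the phrase without the addition.

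**5. Concentration as a predictor.** No SAP analysis uses it. Secondary Aim-4 regresses symptoms on viral load. The Cox model in 5.3.4 lists gender, baseline viral load, age and an open-ended etc.

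**The case against.** Four stronger readings are tempting, and the case against each is good.

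- *The time trend is halved.* The SAP does not exclude an interaction, and comparing change over time implies one. The within-arm summaries would also show the treated profile whichever model is fitted. The halving is therefore conditional. What stands is that the term is named elsewhere and not here.
- *The between-arm p-value is minute whatever the pharmacokinetics.* That assumes complete separation after dosing. A pre-dose Day 1 sample would break it. So could stopped, reduced or delayed dosing (Protocol 4.3, 7.1), and no quantification limit is given. Whether treated participants have measurable levels at all is a basic exposure question, but a treated-arm summary answers it directly.
- *Placebo participants have nothing to measure.* This is an inference. Protocol 5.3 allows supplements in both arms, and Protocol 6.1.1 notes that black seed oil is sold over the counter. Placebo levels could reveal non-study intake, a use the SAP does not state.
- *A planned exposure-response endpoint was dropped.* The protocol sentence is a justification. The objective is basic pharmacokinetics and the endpoint is measurement only. SAP 2.2 allows unlisted exploratory analyses if identified in the study report. The gap is an unspecified analysis, not an unmet endpoint.

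It can also be said that exploratory results are only hypothesis-generating (Protocol 9.4.1). That limits the weight of the point but does not reconcile SAP 5.3.4 with SAP 4.1.3.

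**Conclusion.** The point holds in limited form. SAP 5.3.4 Aim-1 contradicts the population of its own endpoint. Its post-dose between-arm test mainly confirms allocation, and its model leaves open whether the treated slope would be recovered or about halved. The halving requires no arm-by-time term, roughly equal arms and a flat placebo profile; the extreme p-values require complete separation after dosing. The missing concentration-outcome analysis is a gap against the protocol's stated rationale. The aim is exploratory and no primary, secondary or safety conclusion depends on it, so this should be corrected but does not threaten the trial's main results.

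**What to change.** In SAP 5.3.4, Exploratory Aim-1:

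1. Name thymoquinone and its metabolites as the markers, as in SAP 4.1.3.
2. Restrict the summaries and the change-over-time model to participants who took TQ Formula. Alternatively, report the treated-arm slope from a model with an arm-by-time term.
3. Delete the between-arm Wilcoxon test.
4. Add an analysis labelled exploratory, within the TQ Formula arm: the Spearman association, with an interval, of Day 7 and Day 14 concentration with change in log viral load and in symptom score, taking account of recorded time since last dose where available.
5. List any placebo-arm levels only as a check for non-study intake, and do not select samples for assay by allocation before unblinding.

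The cost is SAP wording; no visit or sample changes. The added association has real limits. It is non-randomised and involves at most 30 people. A rough 95% interval around a zero correlation at n = 30 is ±tanh(1.96/√27) = ±0.36. It is also confounded by time since dose: sampling time is not fixed and Protocol 6.1.2 gives a dosing window of ±6 hours. It should stay exploratory.

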#### Analysis plan for Exploratory Aim-2:

Descriptive and graphical statistics will be used to present the distribution of the inflammatory cytokine production, coagulation factors and the various effector immune cell subsets in the Peripheral Blood Mononuclear Cells (PBMC) of all patients on Day 1, Day 7 and Day 14 using FACS within each study arm. These markers will also be compared for differential distribution between the arms using Wilcoxon-Mann-Whitney test. Like above, to compare the change over time in these markers, Random Coefficients Models will be utilized where each of these markers will be the dependent variable and study arm and time will be main predictors.

In addition to the primary analysis described in Section 5.3.2 above, Response Free Survival (RFS) distributions will be compared using Cox-Proportional Hazards Models between the two

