Participants will be randomized to receive either TQ Formula + Standard of Care (SOC) or placebo +SOC

Administer Study Intervention

Participants will be provided with study treatment kit, with enough capsules for 14 days of treatment, 3 capsules BID.

Concomitant Medications and Adverse Events Review

Participants will be assessed for any new adverse events and any changes in concomitant medications

Patient Reported Outcomes

Participants will receive the Modified FLU-PRO Plus questionnaire to complete on a daily basis for the duration of the study, from randomization to final study visit (Day 21).

Subsequent Study Visits (Including Day 21 Final Visit)

Concomitant Medications and Adverse Events Review

Participants will be assessed for any new adverse events and any changes in concomitant medications at each study visit

Physical Exam

A complete physical exam will be performed by the investigator or appropriately qualified designee and documented in the source and in the eCRF at Day 7 and Day 14. A complete physical examination, performed at screening and other specified visits, should include an evaluation of the head, eyes, ears, nose, and throat, and the cardiovascular, dermatologic, respiratory, gastrointestinal, and neurologic systems. Any abnormality identified at baseline should be recorded in the patient's medical records. Limited, symptom-directed physical examinations should be performed at specified postbaseline visits and as clinically indicated. Changes from baseline abnormalities should be recorded in patient notes. New or worsened clinically significant abnormalities should be recorded as adverse events in the patient's medical records.

Vital Signs

Vital signs, including blood pressure (BP), temperature and heart rate will be collected and documented in source and in the eCRF at each study visit.

Serum Collection (Blood sample for immune monitoring)

Blood samples (approximately 15 ml) will be collected for immune monitoring at Day 7 and Day 14, in addition to the baseline visit.

Sample for quantitative viral load testing (RT-PCR)

Participants will have a sample taken for RT-PCR quantitative viral testing at Day 7 and again at Day 14, in addition to the baseline visit.

Laboratory Evaluations (Hematology and Serum Chemistry)

Blood samples (approximately 10ml in total) will be taken for safety laboratory evaluations (as listed in screening above) at Day 7 and 14 and as clinically indicated at any other study visits

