# BOSS-Covid-19 Study (BOSS-001)

## 5.3.3 Secondary Analyses

Analysis plan for Secondary Aim-1:

Secondary estimand-1 is defined to be the slope difference of viral load change overtime between participants taking 3 g TQ Formula (500 mg per capsule, 3 capsules BID) and participants taking placebo regardless of whether or not they actually receive their assigned therapy (ITT) and assuming that their hospitalization and treatment discontinuation rates will be similar.

The first secondary endpoint of this clinical trial is the differential change of viral load distribution overtime between the two-study arm. As the viral load will be measured at Baseline, on Day-7, and on Day-14 (and potentially for some patients in Day-4 and Day-10 visits), the outcome variable of interest will be a longitudinal interval-scale measure. To assess the differential behaviour of viral load overtime between the two study arms, Random Coefficients Models will be utilized where viral load will be the dependent variable and study arm and time will be main predictors. Viral load measures may be subjected to some data transformation (e.g., log transformation) to improve the model fit and assumptions as necessitated by model diagnostics. In addressing this objective, all available data will be utilized; that is, in addition to the evaluable patients, data from non-evaluable patients such as data only at baseline visit or data at baseline and Day-10 for example will be used to improve the local fit of the underlying model. To assess differential behavior in total symptom severity score, time\*study-arm interaction will be investigated as well. The above mentioned intercurrent events, namely, hospitalization (i.e., transitioning from outpatient status to inpatient status) and treatment discontinuation, are applicable for Secondary estimand-1 as well. Therefore, hospitalization-free, while-on-study and per-protocol treatment versions of the above estimand will also be considered within each population definitions above, namely, Full Analysis Dataset (FAS), Final Dataset for Primary Objectives (FDPO), and Per-Protocol Analysis Dataset (PPAS). The above analysis will be carried out using the MIXED procedure of SAS software.

Analysis plan for Secondary Aim-2:

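### SAP 5.3.4, Exploratory Aim-2: the biomarker model states neither the arm-by-time contrast that its purpose needs nor adjustment for the Day-1 marker, and the Wilcoxon test names no visit

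*SAP*

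**What the plan says.** Exploratory Aim-2 (SAP 5.3.4) has three layers.

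- **Description.** Marker distributions are summarised and plotted "on Day 1, Day 7 and Day 14 using FACS within each study arm".
- **Rank test.** "These markers will also be compared for differential distribution between the arms using Wilcoxon-Mann-Whitney test". No visit and no change from baseline is mentioned. The parallel sentence for Exploratory Aim-1 does name the timing: "compared for differential distribution between the arms using Wilcoxon-Mann-Whitney test at each visit".
- **Model.** The purpose is given as "Like above, to compare the change over time in these markers". The tool is a random coefficients model in which "each of these markers will be the dependent variable and study arm and time will be main predictors".

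For the secondary models (SAP 5.3.3, Aims 1 and 3) the SAP uses the same description of the predictors and then adds that the time by "study-arm interaction will be investigated as well". That sentence is absent from both exploratory aims.

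On sampling, Protocol 4.1 says "Blood samples (approximately 15 ml) will be collected for immune monitoring at Day 7 and Day 14, in addition to the baseline visit". Its Baseline Visit list places the immune-monitoring sample ahead of randomization and of dispensing the kit, but never says outright that the blood is drawn before the first dose.

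Nothing else settles the model. Protocol 9.4.9 leaves the exploratory methods to the SAP. Protocol 9.4.7 allows control variables for primary and secondary endpoints only. SAP 5.3.5 promises covariate analyses only where applicable and does not name the baseline marker.

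**The concern.** Comparing change between arms requires an arm-by-time contrast, or a post-baseline comparison adjusted for baseline. Main effects of arm and time give neither. With Day 1 in the outcome and no interaction, the arm coefficient is a weighted average over three visits. One of those visits should show no difference, because it precedes treatment.

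This is the only planned inferential analysis of the objective on inflammatory, coagulation and immune markers. If the contrast is left open, an analyst may report the arm coefficient and understate a real shift, or may choose the contrast after seeing the data. A weak marker result could then reflect the model rather than the product. Separately, every participant already supplies a Day-1 sample that could sharpen the comparison, and neither planned test uses it for that.

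**Working it through.** The documents give no biomarker effect size, SD, correlation or power, so there is no stated figure to reproduce. From the documents: visits at Days 1, 7 and 14 (elapsed days 0, 6, 13); 26 per arm (SAP 3.2); two-sided 0.05 (Protocol 9.4.1). Everything else below is an assumption.

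**Step 1. Arm coefficient without arm-by-time, random intercept.** With balanced data the three visits get equal weight. For a constant effect D at Days 7 and 14 and none at Day 1:

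(0 + D + D)/3 = 0.667D.

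For an effect growing linearly to D at Day 14: (0 + 6/13 + 1)/3 × D = 0.487D. The post-dose mean is then (6/13 + 1)/2 × D = 0.731D, and 0.487/0.731 = 0.667, so one third is again lost.

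**Step 2. Add random slopes.** The expected coefficient is 1′V⁻¹d / 1′V⁻¹1, where d is the vector of true differences and V the within-patient covariance. Early visits gain weight as slope variance rises. With intercept variance 0.6, residual variance 0.4 and d = (0, D, D):

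| Slope SD over 13 days | Weights, Day 1 / 7 / 14 | Arm coefficient |
|---|---|---|
| 0 | 0.333 / 0.333 / 0.333 | 0.667D |
| 0.25 | 0.368 / 0.335 / 0.297 | 0.632D |
| 0.5 | 0.446 / 0.339 / 0.214 | 0.554D |
| 1.0 | 0.597 / 0.347 / 0.056 | 0.403D |

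The pattern matters. For an effect at Day 7 only, the loss relative to the post-dose mean stays near 30–33%.

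**Step 3. Fit arm-by-time instead.** Centred times are −6.33, −0.33 and 6.67, with sum of squares 84.67. For the constant effect, slope difference × 13 = (−0.33 + 6.67)/84.67 × 13 × D = 0.97D. For the linear effect it is 1.00D. So a sustained effect is essentially undiluted. An effect at Day 7 only gives −0.33/84.67 × 13 × D = −0.05D, so a straight-line interaction would miss it. That favours visit as a category.

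**Step 4. What it means for power.** Assume D = 0.8 SD, compound symmetry and 26 per arm (simulated):

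| Analysis | Mean estimate | Power at ρ = 0.3 / 0.5 / 0.7 |
|---|---|---|
| Arm coefficient, all three visits | 0.53–0.54 | 74% / 63% / 56% |
| Days 7 and 14 only, no covariate | 0.80 | 94% / 90% / 86% |
| Day 14 adjusted for Day 1 | 0.80 | 84% / 90% / 97% |
| Wilcoxon, raw Day-14 levels | 0.80 (mean difference) | 78–79% throughout |
| Wilcoxon, change to Day 14 | 0.80 (mean change) | 64% / 78% / 95% |

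With a constant effect and random slopes in both data and model (120 runs per setting, so rough), the arm coefficient had 30–50% power and the arm-by-time term 71–89%.

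**Step 5. The Wilcoxon test.** Raw Day-14 levels return 0.80 for a true 0.80, so there is no dilution. The cost is variance. Relative to raw levels (1), baseline adjustment gives 1 − ρ² = 0.91, 0.75, 0.51 at ρ = 0.3, 0.5, 0.7. A change score gives 2(1 − ρ) = 1.4, 1.0, 0.6, which is worse than raw levels below ρ = 0.5. If the unnamed visit were read as pooling all three, treating repeated values as independent, the type I error is about 16.5% at ρ = 0.5.

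**The case against.** The strongest reply is that the interaction is unstated rather than excluded. The SAP calls arm and time the main predictors, not the only ones. It uses the same phrase for the secondary models, where it does add the interaction, and the declared purpose here is to compare change. This stands. A reader might infer that the plan will certainly understate any marker effect by a third or more. The documents do not support that, because the loss arises only if the arm main effect is the reported contrast.

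A reader might also infer that the Wilcoxon test dilutes the effect. It does not: raw post-dose levels are unbiased under randomization and only precision is lost.

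Keeping Day 1 in the outcome is not an error either. With arm-by-time it is a standard analysis, and it retains patients without a Day-1 value.

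It is also fair that draw time relative to the first dose is inferred from list order. Protocol 8.1 uses the same immune-monitoring blood for pharmacokinetics, and thymoquinone is to be measured on Day 1 in treated patients, so the order needs stating.

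Finally, Protocol 9.4.1 treats exploratory results as hypothesis-generating, and by-arm descriptive summaries at each day would show a large shift. That limits the consequence. It does not supply the missing contrast. The words linking the model to what comes above point most naturally to Exploratory Aim-1, which lacks the interaction too.

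**Conclusion.** The point holds in a limited form. The written Aim-2 model does not state the contrast that its own purpose needs, and neither planned test adjusts for the Day-1 marker.

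- **Conditional loss.** If the arm coefficient is reported, it recovers two thirds of a constant Day 7/14 effect, and about 0.63 to 0.40 of it over the slope SDs tabulated. If arm-by-time is fitted, a sustained effect is essentially undiluted.
- **Unconditional loss.** A raw-level comparison at one visit forgoes the 1 − ρ² variance factor, which is small at ρ = 0.3 (0.91) and substantial at ρ = 0.7 (0.51).
- **Unclear visit.** The Aim-2 rank test should say when it is run, as Aim-1 does.

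The zero Day-1 difference assumes a pre-dose sample. Effect sizes, correlations and slope SDs are assumptions; the averaging in Step 1 needs only a balanced random-intercept model and the stated effect pattern. Because the analysis is exploratory, the priority is low to moderate.

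**What to change.** In SAP 5.3.4, Exploratory Aim-2:

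1. Model the log marker at Days 7 and 14, with the log Day-1 marker as covariate plus arm, visit (as a category) and arm-by-visit. Report the adjusted arm ratio at each visit with a 95% CI. Alternatively, keep Day 1 in the outcome and name arm-by-time as the contrast to be reported.
2. State that the Day-1 immune-monitoring sample is taken before the first dose, and align the Protocol 4.1 wording with this.
3. If the Wilcoxon test is kept, run it separately at Day 7 and Day 14. Do not pool visits, and do not switch to change scores, which lose power when the pre/post correlation is below 0.5.

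The cost is wording only, with no new samples or visits. Patients without a Day-1 value drop out of the covariate model; the alternative in item 1 keeps them.
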